#### 17.4.2.1.2 Analysis

The outcome T will be presented graphically using Kaplan-Meier curves, stratified by treatment group. E=0 denotes a censored observation. Difference between the two treatment arms will be tested using the log-rank test. If there is imbalance in the randomisation, Cox proportional hazards regression may be used to calculate a hazard ratio with 95% CI, comparing the IV treatment group to oral, whilst adjusting for baseline variables for which there is imbalance. From inspection of the Kaplan-Meier plot the separation between the curves should remain proportional across analysis time. If the curves cross again this shows that the proportional hazards assumption has been violated. To put this formally, the proportional hazards assumption is that the ratio of hazards is a constant that does not depend on time:

$$\frac{h_A(t)}{h_B(t)} = r$$
 [Eq1]

When this assumption fails, it is because the hazard ratio changes over time. To test this, we will add predictor for (treatment arm)\*time interaction i.e. a time-dependent covariate. Evidence that (treatment arm)\*time interaction is not zero is evidence against proportional hazards. In SAS, PROC PHREG provides the p-value of this test. p<0.05 will indicate non-proportional hazards and thus a time-dependent covariate will be included in the Cox model. If p<0.05 it may not be possible to present result from which conclusions may be drawn.

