## 12 Confidence Intervals, p-values and Multiplicity

All applicable statistical tests will be two-sided and will be performed using a 5% significance level; confidence intervals presented will be 95%. No adjustment will be made for multiplicity for the secondary outcomes.

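### Time to recurrence: crossing Kaplan-Meier curves do not show non-proportional hazards, and the section lets a conclusive result go unpresented after p<0.05 without guaranteeing any effect estimate

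*SAP*

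**What the plan says.** SAP section 17.4.2.1.2 plans Kaplan-Meier curves by arm and a log-rank comparison: "Difference between the two treatment arms will be tested using the log-rank test". Neither depends on a further check. A hazard ratio is conditional and optional: "If there is imbalance in the randomisation, Cox proportional hazards regression may be used to calculate a hazard ratio with 95% CI".

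Two checks of proportional hazards follow.

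- **Visual.** "From inspection of the Kaplan-Meier plot the separation between the curves should remain proportional across analysis time", and then "If the curves cross again this shows that the proportional hazards assumption has been violated". No size, timing or confidence band is attached to a crossing.
- **Formal.** An arm-by-time term is added to the Cox model as a time-dependent covariate. The stated action is: "p<0.05 will indicate non-proportional hazards and thus a time-dependent covariate will be included in the Cox model". The next sentence is: "If p<0.05 it may not be possible to present result from which conclusions may be drawn".

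The same analysis section governs the two extreme-case analyses added after blind review and the sensitivity analysis in section 19.2.1, which changes the time origin.

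**The concern.** There are two separate weaknesses.

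First, the crossing sentence treats a feature of the estimated curves as proof about the underlying hazards and leaves no room for sampling variation. An analyst who follows it could report a failed assumption in a trial where the assumption holds exactly, most easily where the arms do not differ.

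Second, the closing sentence leaves open whether the first-listed secondary outcome yields a conclusion, and that choice would be made after seeing a test computed on that same outcome. No criterion is given and no numerical between-arm summary is fixed for that case. The log-rank test gives a p-value but no effect size, and a hazard ratio is planned only on imbalance. A changing effect is foreseeable when 14 days of intravenous treatment are compared with 12 weeks of oral treatment (SAP section 8.2), so the plan should say what is reported then.

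**Working it through.** **No stated figure to reproduce.** The SAP gives no sample size, event count or event rate for this outcome; section 10 refers to the protocol. The check is therefore algebra plus simulation over assumed ranges.

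**Algebra.** The section defines proportional hazards as h_A(t)/h_B(t) = r, which implies S_A(t) = S_B(t)^r.

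- If r is not 1, the true curves do not cross after time zero. This is the sound idea behind the sentence.
- If r = 1, the true curves coincide. The estimated difference D(t) = Ŝ_A(t) − Ŝ_B(t) is then noise around zero and readily changes sign although the assumption holds exactly.
- The converse also fails. A hazard ratio moving from 0.4 to 1 is not constant, yet it need not make the curves cross.

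**Inputs from the SAP.** 1:1 allocation (section 8.7); two-sided 5% tests (section 12); 15 months of follow-up for all and up to 24 for some (section 8.9).

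**Assumed inputs.** 60 to 500 patients per arm; control event risk of 10%, 20% or 50% by end of follow-up; 15% early censoring; exponential event times in the proportional-hazards scenarios. Event dates were either continuous or tied to 7 visits. There were 1000-1500 simulated trials per scenario.

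**Definitions.** A crossing means D(t) takes both signs after the first event. The formal test is a two-sided Wald test of γ = 0 in h(t) = h0(t)·exp(βx + γxt), where x is the arm, at 0.05.

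**Result 1: any crossing when hazards are truly proportional.**

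| True hazard ratio | Continuous dates | Tied to visits |
|---|---|---|
| 1 | 70-95% | 58-63% |
| 0.65 | 59-74% | 22-40% |
| 0.5 | 54-61% | 9-28% |

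At a hazard ratio of 1, requiring more than 1 percentage point on both sides lowers this to 44-85% (continuous) or 19-53% (tied). Requiring more than 3 points gives 0-66%.

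A second set of runs used 100-140 per arm, 10-40% recurrence by month 15 and 600 trials per scenario. With sample dates scattered by one week around quarterly visits, any crossing occurred in 76-88% at a hazard ratio of 1 and 72-78% at 0.75. With dates strictly tied to visits the figures were 52-57% and 33-48%. Scattered dates are closer to this trial: event time is taken from the sample date (section 17.4.2.1.1), and section 8.9 reports many visits outside their windows.

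**Result 2: does each criterion separate true from false proportionality?** 20% events, continuous dates.

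| Per arm | Criterion | Hazard ratio 1 | 0.5 moving to 2 | 0.4 moving to 1 |
|---|---|---|---|---|
| 125 | Any crossing | 86-87% | 90-91% | 56% |
| 125 | Arm-by-time test | 4-5% | 48-50% | 20% |
| 250 | Any crossing | 89.7% | 94.5% | 57.3% |
| 250 | Arm-by-time test | 5.5% | 80.7% | 36.9% |
| 500 | Any crossing | 93.9% | 97.9% | 49.5% |
| 500 | Arm-by-time test | 4.6% | 97.3% | 67.2% |

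Any crossing is nearly as common under exact proportionality as under a reversal of effect, and less common under a fading effect than under no effect. The arm-by-time test behaves as a test should. Across the null scenarios it rejects in about 3-7% (0.2% with only about 11 events). At 125 per arm with 20-50% events it detects a ratio moving from 0.5 to 2 in 46-90%.

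**Result 3: how often the non-presentation option is reached.** It hangs on the arm-by-time test, so those rejection rates apply: about 3-7% of trials with no effect, but 46-90% in the reversal scenario just given. The option therefore opens mainly when the effect changes over time, which is when a hazard ratio is least useful and another estimate is most needed.

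**The case against.** The strongest reply is that crossing triggers no action in this plan. Both consequences, adding the time-dependent covariate and the possible lack of a conclusive result, are tied to p<0.05 on the arm-by-time term. A reader might infer that, because curves usually cross under no effect, the result would usually be withheld or the whole rule could not discriminate. The SAP does not support that. The crossing frequencies bear on the visual sentence only, and the formal test has about nominal size and real power.

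A reader might also infer that the plan requires the result to be suppressed. It does not. The clause is permissive and can be read as a caution about interpretation, and the Kaplan-Meier plot and log-rank test stay in place. The log-rank test remains valid under the null of no difference. Where the Cox model is used, the time-dependent term does estimate a changing hazard ratio.

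The crossing percentages also depend on counting every sign change, however small, and on assumed sample sizes and event rates. For a sizeable effect, or with events tied to visits, crossing is often the exception.

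All of this stands and limits the point. It does not rescue the crossing sentence, which is false as stated. Nor does it supply a criterion for the closing sentence, or an effect estimate where there is no imbalance.

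**Conclusion.** The point holds in two limited parts.

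1. The crossing sentence is statistically wrong. With exactly proportional hazards and no effect, estimated curves cross in 58-95% of trials across the main scenarios, and in 52-57% in the lowest supplementary ones. The algebra needs no assumptions. The percentages rest on assumed sample sizes, event rates and censoring, and on counting any crossing.
2. The section leaves an open-ended option, exercised after seeing the data, not to present a conclusive result when the arm-by-time test gives p<0.05. It guarantees no numerical between-arm estimate. Under no effect the option opens in about 3-7% of trials per analysis. It opens far more often when the effect truly changes. Because the section governs several analyses of the outcome, the test can be significant in one and not in another, and no rule covers that.

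This concerns a secondary outcome and does not touch the primary analysis. It warrants a change of wording and one committed estimate.

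**What to change.** In SAP section 17.4.2.1.2:

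- Delete the crossing-curves sentence, or limit it to describing the plot.
- Delete the sentence saying that a result may not be presentable.
- State that, whatever the arm-by-time test shows, each planned analysis of this outcome reports the log-rank result and a between-arm estimate that does not need proportional hazards, with a 95% CI. This applies to both extreme-case analyses and to section 19.2.1. Suitable estimates are the Kaplan-Meier recurrence-free proportions at 15 months with their difference, the difference in restricted mean recurrence-free time to 15 months, or both. Other such measures would also serve, provided one is fixed in advance. Fifteen months is the longest horizon to which all patients were due to be followed (section 8.9).
- Keep the arm-by-time test as a descriptive diagnostic.

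The cost is a few lines of SAP text and one extra estimate per analysis, with no new data.

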#### Update following blind review:

Two analyses of this outcome will be performed. The first analysis will assume that all patients who do not have both a baseline sample and a follow up sample in the time window of interest (T3 to T24) sent for genotyping did not have a reoccurrence of the original *P.aeruginosa* strain (E=0). The second analysis will assume that these patients did have the original *P.aeruginosa* strain reoccur (E=1).

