9.0	2.0	17.4.2.9 .2	Results to be presented at specific time points rather than as change from baseline. This was a recommendation from blind review. Also wording added to clarify that a treatment group*time interaction term would be added to the model.	23/08/18

9.0	2.0	19.1	Sensitivity analyses 1 and 2 amended to include all	23/08/18
			patients that have been followed up past 3 months but not	
			had a sample taken within the 15 month window	
			Sensitivity analysis 3 amended to include patients that	
			have been followed up longer than 15 months but did not	
			have a sample within the 15 months. These patients will	
			be classified as success or failure dependent on the next	
			sample that was taken following the 15 month window.	
			An additional sensitivity analysis added where a logistic	
			regression model adjusted for centre as a random effect	
			will be fitted to investigate heterogeneity across sites.	
9.0	2.0	17.4.2.1	Wording added to explain that two analyses will be	21/09/18
		.2	performed assuming extreme cases for patients who did	
			not have required samples assessed for genotyping. This	
			was a recommendation from blind review.	
9.0	2.0	17.4.2.2	Wording removed that said analysis would be repeated	21/09/18
		.2	separately for each genotype. This was a	
			recommendation from blind review.	

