#### 17.4.2 Secondary outcomes

#### 17.4.2.1 Time to reoccurrence of original *P.aeruginosa* infection

Only patients who have a baseline sample and at least one sample post three months will be included in this analysis.

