#### 17.4.2.1.1 Derivation

Patients will be categorised with a censoring indicator variable E:

E =

- 0: no recurrence of original P.aeruginosa until last available follow-up date; or
- 1: *P.aeruginosa* infection has recurred i.e. if and only if genotype of at least one reinfection sample = genotype of baseline infection sample

A time to event (T) in months will be calculated for each patient as  $T = T_1 - T_0$ , where

 $T_0$  = date of randomisation (CRF: *Treatment CRF*, variable: TATRDTD for patients on IV treatment, OCDTCPSD for patients on oral treatment)

If E=0:

 $T_1$  = date of last available follow-up visit (CRF: *Follow-up*, variable: FUVISITD) If F=1.

 $T_1$  = date of first sample taken during follow-up which indicates E=1 (CRF: *Microbiology Form*, variable: MBDSTD.

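### As written, the second extreme-case genotyping analysis codes patients who never regrew P. aeruginosa as recurrences of the original strain, with no event date, so it does not bound the effect of missing genotypes

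*SAP*

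**What the plan says.** SAP 17.4.2.1 sets the population: "Only patients who have a baseline sample and at least one sample post three months will be included in this analysis". The later sample need not be positive, so a patient who stays culture-negative is included.

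SAP 17.4.2.1.1 defines the event. A patient has E=1 "if and only if genotype of at least one reinfection sample = genotype of baseline infection sample". The event time is the "date of first sample taken during follow-up which indicates E=1". A patient with E=0 is censored at the "date of last available follow-up visit".

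The update following blind review, at the end of 17.4.2.1.2, adds two analyses. They concern "all patients who do not have both a baseline sample and a follow up sample in the time window of interest" (T3 to T24) whose samples were sent for genotyping. The first takes it that patients without such a pair "sent for genotyping did not have a reoccurrence of the original" strain, so E=0. For E=1 it says: "The second analysis will assume that these patients did have the original" strain recur. Neither analysis is ranked above the other.

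The change-control table (Section 1) describes these as two analyses "performed assuming extreme cases for patients who did" not have the required samples genotyped. The Kaplan-Meier curves and the log-rank test of 17.4.2.1.2 are applied to the resulting coding.

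**The concern.** An event under the derivation requires regrowth: there must be a reinfection isolate, and its genotype must match baseline. The update drops that condition. A patient who stays culture-negative from T3 has no reinfection isolate to send, so has no genotyped pair, and the second analysis makes that patient a recurrence of the original strain. Someone followed only to T15 could then be a success on the primary outcome (17.4.1.1) and a recurrence here, over the same follow-up.

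Two things are at stake. First, a pair of extreme-case analyses should bracket the result that full genotyping would have given. This pair does not, because its second member also changes the status of patients whose outcome is not in doubt. Second, these patients have no sample indicating recurrence, so the event time is undefined for what may be half or more of each arm. Whoever programs the analysis must choose a date, and the log-rank result depends on that choice.

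**Working it through.** The SAP gives no event rate, event count or power for this outcome, so there is no figure to reproduce. All rates below are assumptions for illustration.

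**1. Who is left with E=0.** Reading the update with 17.4.2.1 and 17.4.2.1.1, the second analysis gives E=1 to same-strain regrowers, untyped regrowers and all never-regrown patients. Hence

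P(E=1) as written = 1 − P(genotyped, different strain only).

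If the assumption is limited to regrowers,

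P(E=1) limited = P(regrew) − P(genotyped, different strain only).

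The gap between the two is exactly the never-regrown share of the arm.

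**2. Illustration with an equal strain mix.** Assume 60% of IV and 50% of oral patients never regrow. Of regrowers in both arms, 30% are untyped, 35% same strain and 35% different.

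- As written: IV 0.60 + 0.40 × (0.30 + 0.35) = 0.86; oral 0.50 + 0.50 × 0.65 = 0.825.
- Limited to regrowers: IV 0.40 × 0.65 = 0.26; oral 0.50 × 0.65 = 0.325.

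The order of the arms swaps, and 60% and 50% of the arms are false events.

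**3. Same regrowth, but equal new-strain infection.** Assume instead that 15% of each arm are genotyped with a different strain.

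- As written: 1 − 0.15 = 0.85 in both arms.
- Limited: 0.40 − 0.15 = 0.25 v 0.50 − 0.15 = 0.35.

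Here the arms do not swap. The analysis as written shows no difference where the limited one shows 10 percentage points.

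**4. No regrowth genotype missing.** Take 100 per arm, regrowth 30 v 50, all typed, 60% original strain. With nothing missing, both extreme cases should equal the truth.

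- First analysis: 0.60 × 30 = 18 v 0.60 × 50 = 30 (ratio 0.60).
- Second as written: 18 + 70 = 88 v 30 + 50 = 80 (ratio 1.10).

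**5. Effect on the time-to-event comparison.** Simulation, 100 runs per scenario. Assumptions: 120 per arm; regrowth 30% v 50% or 40% v 55%, uniform over 3–15 months; 50% or 80% of regrowths the original strain; 50% or 90% of regrowths typed; baseline always typed; half of patients followed to 15 and half to 24 months; same strain mix in both arms. Results for the second analysis as written, by the date given to never-regrown patients:

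| Imputed date | HR, better arm | HR above 1 (runs) | HR above 1 and p<0.05 (runs) |
|---|---|---|---|
| About 3 months | 1.25–1.44 | 96–100% | 35–76% |
| Uniform, 3–15 months | 1.04–1.25 | 61–95% | 4–35% |
| Last follow-up | 0.82–1.00 | 9–50% | 0–3% |

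Events were 82–97% of the better arm and 74–95% of the other. Limited to regrowers, the HR was 0.50–0.58 (30% v 50%) and 0.64–0.69 (40% v 55%). This is close to the first analysis, at 0.52–0.60 and 0.65–0.71.

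**The case against.** The strongest reply is that this is a drafting omission. The change-control entry speaks of required samples, and a culture-negative patient has no reinfection isolate that could be required. That may well be the intention, but the update does not say it, and the analysis will be programmed from the update. The SAP also does not state which samples go for genotyping; that negative cultures are not sent is inferred from the event definition. The protocol may settle it.

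For regrown patients whose isolates were not typed, E=1 is a legitimate worst case. The fault is confined to the missing regrowth condition.

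A reader might infer that the comparison will reverse. The documents do not support that. The swap in proportions needs a similar strain mix among regrowers in both arms (step 3 removes it). The log-rank direction depends on a date that the SAP does not define: at last follow-up the usual effect is attenuation.

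A reader might also infer that the update admits patients without a baseline sample, against 17.4.2.1. This is not shown. The words about being sent for genotyping can govern both samples, so the update can be read as dealing with untyped samples within the population that 17.4.2.1 has already fixed.

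Finally, the outcome is secondary, the first analysis codes culture-negative patients correctly, and the primary outcome does not use genotype. All of that stands and limits the severity.

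**Conclusion.** Wrong as written; should be fixed. The second analysis turns patients who stay culture-negative after T3 into recurrences, gives them no event date, and leaves E=0 only for patients genotyped with a different strain. It is therefore uninformative as a worst case for missing genotypes. This follows from the text alone, given the inference that culture-negative samples yield nothing to genotype.

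The size rests on assumed rates. The false events equal the never-regrown share of each arm, 60% and 50% in the illustration. The comparison can be reversed, flattened or merely attenuated, according to the strain mix in each arm and the date chosen. One of the two planned analyses of this secondary outcome is affected.

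**What to change.** In the update to 17.4.2.1.2:

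- Apply both extreme assumptions only to patients in the 17.4.2.1 population who have at least one positive P. aeruginosa culture between T3 and T24 and no genotyped baseline/follow-up pair.
- For an imputed E=1, set T1 to the date of the first such positive culture.
- Keep culture-negative patients at E=0 in both analyses, censored by the existing rule in 17.4.2.1.1 (last available follow-up visit).

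The inclusion rule in 17.4.2.1 and the censoring rule need no change. The cost is a few words in the SAP and one condition in the derivation program. Culture results and sample dates are already on the Microbiology Form, so no new data are needed.

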#### 17.4.2.2 Re-infection with a different genotype of P.aeruginosa

#### 17.4.2.2.1 Derivation

This outcome is derived using the Microbiology CRF, and includes only samples taken at or after  $T_3$  or at or before  $T_{15}$ . A binary variable: *P.aeruginosa* infection with a different genotype of *P.aeruginosa* is defined as: genotype of at least one re-infection sample  $\neq$  genotype of baseline infection sample, Yes/No. Where the genotype of the baseline sample is unknown / not available, it will not be possible to derive this outcome.

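### The extreme-case rule for time to recurrence depends on samples being sent, not on regrowth without a valid genotype, so it varies E for the wrong patients

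*SAP*

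**What the plan says.** SAP 17.4.2.1 sets the analysis population: "Only patients who have a baseline sample and at least one sample post three months will be included in this analysis". It asks for samples, not for genotype results.

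SAP 17.4.2.1.1 gives E=1 "if and only if genotype of at least one reinfection sample = genotype of baseline infection sample". An event is dated at the first follow-up sample that shows the match. A patient with E=0 is followed to the last available visit, and under 17.4.2.1.2 "E=0 denotes a censored observation".

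The update following blind review, in 17.4.2.1.2, adds two analyses. The group concerned is defined as "all patients who do not have both a baseline sample and a follow up sample in the time window of interest", a window that the update gives as T3 to T24. The first analysis assumes that patients lacking such a pair "sent for genotyping did not have a reoccurrence of the original" strain, that is E=0. For the other extreme, "The second analysis will assume that these patients did have the original" strain recur, that is E=1. Nothing is said about samples that were sent but gave no usable result, or about the date of an assumed event.

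For the companion outcome, re-infection with a different genotype, SAP 17.4.2.2.1 does foresee an unknown type: "Where the genotype of the baseline sample is unknown / not available, it will not be possible to derive this outcome". Time to recurrence has no such sentence.

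**The concern.** The two analyses are the SAP's only specific handling of unknown strain for the first-listed secondary outcome in section 9.2. They should vary E for patients who regrew *P. aeruginosa* and whose strain cannot be compared with baseline, and for nobody else. The stated trigger misses this group on both sides:

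- It leaves out patients with regrowth whose strain is unknown although a pair was sent.
- Read literally, it takes in patients without regrowth, who had no follow-up isolate to send and whose status is not in doubt.

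If reported as extreme cases, the results could be taken to cover the missing-genotype uncertainty when part of it is held fixed and part of the apparent range does not come from missing genotypes at all.

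**Working it through.** The SAP states no figure here, so there is none to reproduce. The check applies 17.4.2.1.1 and the update to each type of patient. It assumes that only a *P. aeruginosa*-positive sample can be sent for genotyping.

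| Patient from T3 to T24 | Recurrence status | E as written (first / second) | E with the fix (first / second) |
|---|---|---|---|
| Regrowth, pair not both sent | unknown | 0 / 1 | 0 / 1 |
| Regrowth, pair typed, match | known | 1 / 1 | 1 / 1 |
| Regrowth, all isolates typed, all different | known | 0 / 0 | 0 / 0 |
| Regrowth, pair sent, no valid type | unknown | 0 / 0 | 0 / 1 |
| One regrowth typed as different, another not sent | unknown | 0 / 0 | 0 / 1 |
| No regrowth, so no isolate to send | known, no recurrence | 0 / 1 | 0 / 0 |

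The fourth and fifth rows should vary and do not. The fifth arises because 17.4.2.1.1 asks whether at least one reinfection sample matches, while the update is satisfied once a single follow-up sample is sent. The last row should not vary and does.

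**Effect on the counts.** Let M be demonstrated matches, S patients with regrowth but no sent pair, u the patients in rows four and five, and w those in the last row.

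- First analysis: M events, both as written and with the fix.
- Second analysis as written: M + S + w.
- Second analysis with the fix: M + S + u.
- Error in the second count: (M + S + w) − (M + S + u) = w − u.

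The sign depends on which group is larger, and the SAP gives neither.

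**Illustration of u alone.** All inputs are assumed: 30 sent pairs, a share f failing typing, and 50% matching among typed pairs. The lower count is 30 × (1 − f) × 0.5; the upper count adds the 30 × f failed pairs.

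| f | Failed pairs | Lower | Upper |
|---|---|---|---|
| 0% | 0 | 15.0 | 15.0 |
| 5% | 1.5 | 14.25 | 15.75 |
| 10% | 3 | 13.5 | 16.5 |
| 20% | 6 | 12.0 | 18.0 |
| 30% | 9 | 10.5 | 19.5 |

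As written, both analyses give only the lower value for these pairs. The gap equals the number of failed pairs whatever the match share. At f = 10%, for example, it is 3 for a match share of 30% (8.1 to 11.1) and of 80% (21.6 to 24.6). With u = 3, the second count is too low if w is below 3, correct in total if w = 3, and too high if w is above 3.

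**Event date.** For E=1, 17.4.2.1.1 takes T1 from the sample that demonstrates the match. An assumed event has no such sample, so T1 is undefined and the Kaplan-Meier and log-rank analyses cannot be run for it without a further decision.

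**The case against.** **The SAP does not say that an untyped pair is E=0.** The E=0 category is worded as no recurrence of the original strain, which has not been shown for such a patient. SAP 17.1 limits analyses to participants whose outcome was observed and rules out imputation, and 17.4.2.2.1 treats an unknown baseline genotype as not derivable. Exclusion is therefore a tenable reading. This stands as a point about wording, but it does not cure the problem: an excluded patient is not varied between the two analyses either.

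**The change log may show a wider intent.** SAP section 1 describes the same update as covering patients who did "not have required samples assessed for genotyping". A reader might infer a contradiction with the operative text. The documents do not support that: a change log is a summary, and a difference from the current text is not an error. At most it suggests that the intended group was wider than the rule as written.

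**A reader might infer that the range is too narrow and the log-rank result falsely robust.** That does not follow. The same sentence, read literally, adds patients without regrowth as events in the second analysis, which widens the range. The error is w − u and its sign is unknown.

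**The size is unknown and may be nil.** This stands for the omitted group. Nothing in the SAP says that any sent sample failed typing or that any second regrowth went unsent. If neither occurred, u is zero.

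**Conclusion.** The rule uses the wrong trigger for unknown strain. It leaves fixed, or drops, patients with regrowth whose strain is unknown although a pair was sent. Taken literally, it makes events of patients without regrowth, and it leaves assumed events undated. These conclusions follow from the SAP's wording, with one assumption: a sample without *P. aeruginosa* cannot be sent for typing.

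No size or net direction can be given. The counts above rest on assumed inputs and show only how the error behaves.

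Nor should correction be taken to bound the comparison between arms. Both arms receive the same assumption in each analysis, so even with the right patients the pair bounds the recurrence count within each arm, not the treatment difference or the log-rank result. The point concerns one secondary outcome and leaves the primary analysis untouched. It is worth correcting because a stated rule assigns patients wrongly and the remedy is short.

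**What to change.** Replace the update in 17.4.2.1.2 with a rule to this effect:

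- Apply the two assumptions only to patients who have at least one *P. aeruginosa*-positive sample from T3 to T24, no demonstrated match with baseline, and no valid genotype for the baseline isolate or for at least one positive follow-up isolate.
- In the first analysis, set E=0 for these patients.
- In the second, set E=1, dated at the first untyped regrowth, or at the first regrowth if the baseline isolate is untyped.
- Keep patients without regrowth at E=0 in both analyses. Patients with a demonstrated match keep their event and date.
- Describe the pair as bounding the recurrence counts in each arm, not the treatment difference.
- Report, by arm, how many patients fall under the assumption and why: not sent, or sent without a valid result.

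The cost is a few sentences in the SAP and a change to the derivation program, using data already collected. The range between the two analyses may become wider or narrower, depending on how many patients are in each misassigned group.
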